9.4. RECORDS RETENTION	29
10. STUDY MONITORING, AUDITING, AND INSPECTING	30
10.1. STUDY MONITORING PLAN	30
10.2. AUDITING AND INSPECTING	30
11. ETHICAL CONSIDERATIONS.....	30
11.1. CONFLICT OF INTEREST.....	30
11.2. SUBJECT STIPENDS OR PAYMENTS	31
12. REFERENCES.....	31

Study Summary

Title	Adaptive deployment of DermAI to evaluate human factors of testing
Running Title	User Adaptation
Protocol Number	DermAI-005
Phase	Other
Methodology	Prospective randomized controlled trial
Overall Study Duration	12 months
Subject Participation Duration	Participation will take approximately 1 week.
Single or Multi-Site	Single
Objectives	To develop the performance characteristics and human factor considerations to support fully remote patch testing.
Number of Subjects	Up to 10 pilot subjects followed by 150 Adaptive Patients
Diagnosis and Main Inclusion Criteria	
The condition being studied is allergic contact dermatitis
 
Inclusion Criteria:
 
 • Adults aged 18 or older • Able to provide consent
Study Product, Dose, Route, Regimen	
Device: AI algorithm to evaluate photographs of skin test patch regions
 
Drug: Allergens used in the testing protocol

Statistical Methodology	The analysis plan will focus on comparing the AI predictions of reactions with the interpretation of a human review of the photographs documented during the study visits. The reference criterion will be the expert, in person review as is currently performed with standard clinical operations.

Summary of Protocol Changes

Protocol Version	Summary of Key Changes
1.0	
• Original Protocol
1.1	
• Addition of 10 pilot subjects• Minor refinements to protocol details throughout
1.2	
• Addition of allergens and updates on Phase III activities.

1. Introduction

This document is a protocol for a human research study. This study will be carried out in accordance with the applicable United States government regulations and Mayo Clinic research policies and procedures.

1.1. Background

Allergic contact dermatitis is a common inflammatory skin disorder. The disorder is characterized by pruritus, erythema, vesicles and scaling of the skin. Contact dermatitis can be further divided into allergic contact dermatitis (ACD) and irritant contact dermatitis (ICD). ACD is a type of IV-mediated hypersensitivity to a specific allergen, resulting in an inflammatory response with exposure. ICD is a non-immunologically driven, inflammatory reaction to an irritating substance.

ACD is common, with some studies demonstrating prevalence rates as high as 20% of the general population (Alinaghi, Bennike, Egeberg, Thyssen, & Johansen, 2018). It can be difficult to distinguish ACD from other forms of dermatitis. History, patch testing, and other forms of assessments may help to clarify the diagnosis.

The cause of allergic contact dermatitis is determined by patch testing performed by dermatologists.

1.2. Investigational Agents

This protocol is in preparation of the creation of an integrated test kit consisting of a novel physical patch design, custom allergen panels, digital photography, and a computer vision-based algorithm to interpret the patch test results. These innovations represent a future state of technology. Within scope of this protocol is an adaptation of existing patch testing supplies and a test of the performance of the AI algorithm performance in a manner that does not inform or alter the routine clinical diagnostic practice to minimize risk.

The prospective data collection will involve multiple digital photography technologies. The primary photography device is an iOS-based custom application that allows for automated photograph capture and scheduling. This smartphone application will be used by the participant enrolled in the study using a study-specific iPhone 12 or newer device. The application in its current state only photographs the test site region and uploads the images to a secure, Firebase database on Google Cloud. The software as a medical device aspect of the AI processing will not be involved in the capture or transfer of the data in the current configuration. The models will be run asynchronously using the data captured during the study. In addition to this smart phone application, we will also use additional cameras, including a full-spectrum (infrared + ultraviolet + visible light spectrums), to ensure the model performance is not contingent upon the iPhone model used in the study along with providing new data to potentially enhance the detection of contact dermatitis in the future.

1.2.1. Camera technologies under study

Visible Light Digital Photography (“regular” photography): A standard iOS camera system will be the primary camera used in the study. This camera will be supplemented with cameras used during routine clinical documentation of the testing (i.e., a combination of Mayo Clinic owned and operated smartphones and interchangeable lens cameras).

Full Spectrum Photography: A full-spectrum digital photography system is one where the digital sensor has had the Bayer filter removed. This allows all wavelengths of light to reach the imagining sensor, including the ultraviolet spectrum (not visible with the unaided eye). A “Wood’s light” (or black light) uses ultraviolet light to accentuate different aspects of the skin, particularly pigmentation profiles. The study will also need to incorporate infrared light sources to best utilize the spectrum of light energy a camera can capture. A full spectrum camera can photograph the same wavelength of light, particularly if a glass filter that allows only a narrow range of wavelengths to pass is used. Likewise, infrared is used by many animals (and door sensor technologies) to identify subtle differences in heat profiles in objects. We are hypothesizing that the combination of ultraviolet and infrared spectra will improve the detection of allergic contact dermatitis by the computer vision algorithms.

[figure not shown]
Photogrammetry: While a single photograph may characterize the appearance of raised textures on the skin surface, photogrammetry allows for direct modeling of the surface of the skin. Briefly, photogrammetry is an established technique where an object (e.g., a suspicious skin lesion) is photographed from 30 or more angles. Computer algorithms assemble the set of photographs into a 3D mesh object that is a digital representation of the surface of the skin. We hypothesize that this 3D representation of the skin lesion will convey important “tactile” information about the test sites that is not otherwise present in standard 2D digital photographs.

1.2.2. Allergens

The use of the allergens are in accordance with standard clinical practice. However, the allergens are not FDA approved for this purpose. As such, they will be considered as investigational agents in the context of this study.

1.2.3. Test Patch

The physical patch test device is a clinical standard apparatus manufactured by Finn Chamber. The allergens are applied to the skin by means of direct contact when the patch test device is applied for testing. Allergens are contained in an inert metal well. For the purpose of this study, the paper-like border surrounding these metal wells will be modified to allow for specific visual patterns to be drawn onto the skin using a standard surgical marker (blue shaded regions in the figure below). These markings will allow for the finalized AI workflow to identify unique allergen placement profiles based on markings drawn on the skin.

[figure not shown]
1.3. Preliminary Data

1.3.1. Study #1: IRB 19-012164

[figure not shown]
To-date, retrospective data collection under IRB 19-012164 has enrolled 310 subjects with 5,417 reaction photographs (approximately 54,170 individual reaction sites) which includes images taken both from the prior patch design as well as the new, fiducial patch design.

We have designed a deep learning classifier to predict the presence of allergic reaction from smartphone images of patch test reaction sites. The model was tested on a dataset of 260 patches (2,600 individual reactions) from several dozen individuals.

On the test dataset, the model displayed area under the ROC curve of 0.877. At a prediction cutoff of 10%, the model had an accuracy of 0.942, a sensitivity (true positive rate) of 0.540, and a specificity (true negative rate) of 0.956. The ROC curve is shown below, along with several examples of correct and incorrect predictions.

ROC curve for model performance at the reaction level

Examples of model prediction. For each of the four examples, the smartphone image of the reaction site is shown on the left, the true reaction label (based on the clinical report) is shown in the middle, and the model prediction is shown on the right. Positive and negative predictions are shown on a continuous color scale, where 1 (red) indicates the presence of reaction and 0 (blue) indicates the absence.

1.3.2. Study #2: Prospective Clinical Trial (IRB 21-011596)

A prospective, pragmatic clinical trial was designed to advance the technologies associated with a democratized skin patch testing approach that leveraged novel patch designs and an integrated smartphone-based application to capture and upload photographs of the patch testing sites to the cloud. The study incorporated an in person, clinical assessment at all three study visits to establish the reference criterion according to current clinical protocol. Photographs were captured at each visit to provide means to evaluate a novel deep learning model for the detection of allergic contact dermatitis. While the deep learning algorithm's performance could be established relative to the in-clinic reference reading, it was unknown just how well a human reader could function when only exposed to the photographs of the test sites (i.e., not able to palpate suspicious regions). To address this, the study incorporated a human reading protocol where the same photographs, void of any data collected about the patient or information obtained during the clinical visit, were reviewed by humans to determine what the accuracy of the machine learning approach in the context of human readers.

A total of 232 participants consented to participate and 206 reached the day five assessment. A specific purpose of this study was to enroll 50% of participants with Fitzpatrick Skin Types IV – VI. This objective was achieved as the distribution of skin types over the six types were as follows: 46.6% were classified as types IV-VI. The mean (SD) participant age was 39.1 (13.5) years, and 66% (136/206) of the participants were female. A total of 32.0% (66/206) of participants self-identified as being Black or African American, 16.5% (34/206) as Asian (34/206), and 40.3% as White (83/206). A total of 23 participants self-identified as Other (11.2%) or of Hispanic origin (73.9%, 17/23).

The overall incidence of allergic contact dermatitis in the sample was 6.4% (132/2,060) using the panel of allergens to be tested in the present study. The 206 images yielded 2060 test sites that were expertly evaluated during the in clinic (Day 5) evaluation. The only input to the neural network was the cropped image of the patch test site sites. The CNN model diagnosed the presence or absence of reaction with an AUROC of 0.861 (95% CI, 0.824 – 0.897). Using the previously selected cutoff of 4.88%, this generated an accuracy of 91.0% (95% CI, 89.7%-92.2%), a sensitivity of 58.3% (95% CI, 49.4%-66.8%), and a specificity of 93.3% (95% CI, 92.0%-94.3%).

1.4. Risks and Benefits

The risks of this research study are minimal. The most common side effect of skin testing is slightly swollen, red, itchy bumps (wheals). These wheals may be most noticeable during the test. In some people, though, an area of swelling, redness and itching may develop a few hours after the test and remain for a couple of days.

Rarely, allergy skin tests can produce a severe, immediate allergic reaction.

The patches are placed on the forearm for 48 hours. During this time, bathing and activities that cause heavy sweating need to be avoided. Irritated skin at the patch site may indicate an allergy.

As with all research, there is a chance that confidentiality could be compromised; however, we will take all appropriate precautions to minimize this risk.

2. Study Objectives

2.1. Primary Objective

- To test if interpretation using novel AI algorithms analysis of photographs of skin patch tests is concordant with in person skin patch test interpretation.

2.2. Secondary Objectives

- To test if human review of photographs of skin patch tests are concordant with in person examination results.
- To demonstrate performance of DermAI application usage by the participant.
- To develop a database on novel photography modalities and explore performance advantages full spectrum photography and photogrammetry may bring to detecting contact dermatitis reactions.
- To explore novel combinations of allergens to lessen the burden of testing.
- To refine and optimize the lighting characteristics for photographing with visible spectrum and full spectrum lighting.

3. Study Design

[figure not shown]
3.1. General Description

The overall adaptive study is designed to include three consecutive phases. Prior to the start of the adaptive study, a pilot cohort of up to 10 participants are planned to optimize the study protocol logistics, including camera usage, image capture parameters and documentation, and lighting conditions. This pilot phase is to ensure that the data captured during the adaptive study are as optimal as possible based on all study procedures. Pilot subjects will undergo the same overall protocol scheme shown below and receive remuneration. The data collected will be used to refine the protocol, with amendments as necessary.

Each of the phases in the adaptive study is intended to advance the technologies and evaluate how scalable the technologies will be outside the clinical practice. The phases described below cover the primary intended workflow using the Mayo Clinic owned iPhone. Additional protocol actions including additional photography and ascertainment of other clinical study data (including adverse events) will occur to enrich the study data.

Common study flow for all phases of the study:

On day 1 a routine skin examination will be conducted. This will include photographic documentation of the condition of the skin region to be tested. Afterwards, the test patches will be applied to commence the testing. On day 3, the patients will return to remove the patch tests and document the test sites using the study iPhone app and the additional camera setups as specified in the protocol. On day 5, the final photographic documentation will be acquired and the final clinical assessment for allergic contact dermatitis will be provided by a medical professional with training in patch testing to establish the reference criterion.

Specific adaptation according to each phase of the study:

Phase 0 (n <=10): This pilot phase will study up to 10 participants to optimize the study manual of operations, ensuring the logistics and timing of all study visits to optimally conduct the three main phases of the study.

Phase 1 (n=100): Phase 1 initiates where the prior pragmatic clinical trial (NCT053339750, IRB 21-011596) concluded. This phase of the study will advance the technology in material ways through shifting day 3 (patch removal) and day 5 (final photographic documentation of test site) to the participant in the study. Participants will be guided in the use of the application and primary iOS/iPhone photographic documentation; the study team will provide additional photographic documentation and review of the test site to establish the reference criterion.

Phase 2 (n=25): For phase 2, the patch will be placed on the inside of the arm by the participant. The study documentation will proceed identical to Phase 1.

Quality Checkpoint Decision: Patch able to be successfully applied by patient in >90% of the cases (fewer than 3 placement errors).

Phase 3 (n=25): In phase 3, the entire study will be patient-led, although on-campus visits will be required to obtain the allergen panel and evaluate the reference criterion. This phase will use a prototype novel test kit with printed instructions and necessary supplies to clean the arm, assemble the patch application jig, install the app, and perform the patch testing. Human observation and patient surveys will be conducted to evaluate the human factors aspects of the test kit.

For both Phases 2 and 3, participants will be invited to complete the Patient Journey questionnaire at least a week ahead of the scheduled visit 1 appointment by email. Responses will be summarized to suggest allergens that would be recommended based on past exposures. The recommendations will be constrained to only the set of allergens tested in this protocol (See Section 5.2). Participant will have the option to select the standard allergens used in Phase 1 of the study or use up to 10 of the recommended allergens based on the Patient Journey.

3.2. Number of Subjects

Up to a total of 160 participants will be enrolled and tested as part of the pilot (n<=10) or adaptive study (n=150).

3.3. Duration of Participation

An individual participant will require three visits to the study site on Days 1, 3 and 5.

3.4. Identification of Source Data

Study-specific case report forms (CRFs) will be used to document all of the following:

1. Demographics and medical history including assessment of Fitzpatrick skin types
2. Patient will be assigned to one of the randomized allergen templates that will be used for the study.
3. Documentation of the randomized location of the allergens on the test patch used with the participant
4. Documentation of the reference criterion (in person assessment by medical professional with training in patch testing Day 5) as well as the initial impression of reactions at Day 3 immediately following the removal of the patches.
5. Participant feedback on the user experience of the test patching
6. Documentation of the blinded human review of the photographs acquired on Day 3 and Day 5
7. Adverse events

The following source data will not be directly collected in the CRFs, but will be integrated into the master database:

- Test site photographs
- AI predictions on the photographs

4. Subject Selection Enrollment and Withdrawal

4.1. Inclusion Criteria

- Adults aged 18 or older
- Willing and able to provide informed consent

4.2. Exclusion Criteria

- Under 18 years of age
- Has used topical or oral steroids two weeks prior to patch testing
- Currently taking immunosuppression agents or is immunocompromised due to medical condition
- No sunburn or rash at site of testing
- Women who are breastfeeding or pregnant.
- Treatment with ultraviolet (UV) light (including tanning) during the two weeks prior to visit.
- Subjects unable to comply with patch test study requirements including multiple return visits and activity restrictions (e.g., protecting patch test area from excess moisture due to showering)

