4.3. Subject Recruitment, Enrollment and Screening

The recruitment for this study will include participants from Mayo Clinic Florida patients and staff, and collaboration with the University of North Florida.

In 2019, approximately 284 patients had skin patch tests performed at Mayo Clinic Department of Dermatology in Jacksonville Florida. Among these patients, 17 were identified Black or African American with a Fitzpatrick score of 5-6, and 32 were identified as Hispanic or Latino with a Fitzpatrick score of 3-6.

Additionally, we will advertise for a healthy control group throughout Mayo Clinic Florida campus as well as the University of North Florida. In 2019, the University of North Florida student population enrollment was reported at approximately 17,117 students. The distribution of population for minority population of interest is 10% (1,684) Black or African American, 13.3% (2,280) Hispanic or Latino, and 5% (853) two or more races. Potential participants can contact the study coordinator listed in the flyer and/or electronic display to further inquire on eligibility criteria and study questions.

Thus, we estimate that from a pool of 49 eligible patients in Mayo Clinic Florida per year, the robust minority population of employees at Mayo Clinic and student population at University of North Florida, we can achieve full enrollment.

We will monitor enrollment bi-weekly and will hold calls with the study team to clarify questions about eligibility and ensure robust recruitment. If recruitment falls short of numerically defined targets, we will assess reasons for slow accrual and adjust the protocol accordingly.

Patients who have undergone previous patch testing will be screened by an experienced study coordinator for participants with a Fitzpatrick skin types 4 through 6 and eligibility criteria. This study coordinator will call the patient to discuss the study, eligibility, and study logistics, and then will plan to meet the patient at their next visit to the clinic to review and sign the consent (if the patient wishes to participate and is eligible).

Potential participants who answer the advertisement will have a call scheduled with the study coordinator to discuss the study, eligibility, and study logistics. Based on the potential participant's agreement, the study coordinator will schedule a research visit, as well coordinate with the Dermatology medical assistants to schedule the patch testing procedures.

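### Nothing in eligibility or the analysis set keeps people whose images built the AI model out of the primary AI-versus-human comparison

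*Combined protocol and SAP*

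**What the plan says.** Section 4.1 asks for adult age and "Willing and able to provide informed consent". Section 4.2 lists seven exclusions, ending with "Subjects unable to comply with patch test study requirements including multiple return visits and activity restrictions". None concerns earlier patch testing, the two earlier studies or an earlier phase of this one.

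Section 4.3 describes two streams. In the clinic stream, "Patients who have undergone previous patch testing will be screened by an experienced study coordinator", with Fitzpatrick types 4 to 6 sought, and "This study coordinator will call the patient to discuss the study, eligibility, and study logistics". In the other, "we will advertise for a healthy control group throughout Mayo Clinic Florida campus as well as the University of North Florida". The clinic stream is small: "we estimate that from a pool of 49 eligible patients in Mayo Clinic Florida per year".

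On the earlier data, section 1.3.1 reports that "retrospective data collection under IRB 19-012164 has enrolled 310 subjects with 5,417 reaction photographs". It describes a test set of 260 patches from a few dozen people but not the development set. Section 1.3.2 reports 232 consenting participants, 206 of them assessed at Day 5, and an AI accuracy of 91.0% at a 4.88% threshold chosen beforehand. Section 1.3.1 had used 10%. Section 3.1 links the studies: "Phase 1 initiates where the prior pragmatic clinical trial (NCT053339750, IRB 21-011596) concluded".

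Section 7.2.2 defines the primary test as AI versus human photo reading, on binary accuracy against the in-person assessment, with a 5-point limit. Section 7.3.5 admits anyone randomized who has the Day 5 assessment.

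**The concern.** A diagnostic model should be evaluated on people who played no part in building it. Here the plan directs a coordinator to previously patch-tested patients, the retrospective image set consists of patch-test photographs, and no step compares the two lists. Section 5.6 blinds the human photo reader but does not address separation of test participants from AI development data. The source-data list in section 3.4 has no specific item for prior participation, so an overlap might not be visible afterwards.

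The direction of the bias is what matters. The human reader gains nothing from the model having seen a participant before, so any benefit moves the AI-human difference toward a finding of non-inferiority. It would also overstate how the AI performs in new users, for whom the technology is intended.

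A smaller matter is re-entry between phases. Phases 2 and 3 examine self-application and the human factors of the kit, and those results describe new users only if the participants are new.

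**Working it through.** The plan states no figure on this point, so there is none to reproduce. The check is a reading of the rules, followed by an illustration of scale.

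**Rules side by side**

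| Place | Does it separate participants from development data? |
|---|---|
| 4.1 Inclusion | No: age and consent only |
| 4.2 Exclusion | No: seven items, none relevant |
| 4.3 Recruitment | No: one stream seeks previously tested patients |
| 5.6 Masking | No: covers the human photo reader |
| 7.3.5 Analysis set | No: randomization and Day 5 assessment only |

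The documents also do not say whose data set the 4.88% cutoff, or whether the model was retrained after the earlier trial.

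**Scale on the primary endpoint**

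Inputs: accuracy 91.0% (section 1.3.2). The overlap share f and the accuracy a in overlapping people are not in the documents; both are assumed.

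Pooled accuracy = (1 − f) × 91.0 + f × a, so the gain is f × (a − 91.0) points.

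| f | a = 95% | a = 100% |
|---|---|---|
| 10% | 0.10 × 4 = 0.4 | 0.10 × 9 = 0.9 |
| 20% | 0.20 × 4 = 0.8 | 0.20 × 9 = 1.8 |
| 49% | 0.49 × 4 = 2.0 | 0.49 × 9 = 4.4 |

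The last row is an extreme bound: all 49 pool patients among the 100 in Phase 1, and all of them in the development data. With no matching human gain, the AI-human difference shifts by the same amount. For the 10-20% rows this is 0.4/5 = 8% to 1.8/5 = 36% of the non-inferiority limit.

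**Re-entry**

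The counts 10 + 100 + 25 + 25 = 160 match section 3.2. Three visits (3.3) and about one week of participation (Study Summary) suggest one pass per person, but no sentence requires it.

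**The case against.** The strongest reply is that overlap is possible but not shown. Section 4.3 also recruits staff and advertises to campus and university volunteers, and the clinic pool is 49 a year. The documents do not say where the 310 retrospective subjects came from or which of them were used for training. That the total exceeds the 284 patients patch tested in Jacksonville in 2019 says nothing about overlap. The mechanism may also be weak: the photographs will be new, allergen positions are randomized, a shell standardizes lighting and distance, and in the earlier trial the network saw only the cropped site. A gain would need learning specific to the person. All of this stands, and it limits the size that can be claimed. It does not supply the missing rule.

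Three stronger readings are tempting and are not supported:

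- A reader might infer that the model has learned from the participants of the earlier prospective trial. Section 1.3.2 presents that trial as an evaluation at a cutoff already fixed. Whether its images were used later is not stated.
- A reader might multiply an overlap of 10-40% by a sensitivity gain of 5-20 points and report an inflation of 0.5-8 points. Neither input is in the documents, and the primary endpoint is accuracy. At the planned 15% positive sites, the same gain is 0.15 × 0.5 = 0.075 to 0.15 × 8 = 1.2 accuracy points.
- A reader might infer that two or three returning users could decide the Phase 2 checkpoint, which allows at most 2 errors in 25. In section 3.1 self-application first appears in Phase 2, so someone returning from Phase 1 would know the app but would not have practised placement. Even with three error-free users and an assumed 15% error rate in the others, the chance of passing rises only from 25.4% to 33.8%.

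**Conclusion.** The gap is real: as written, the plan allows people from the model's development data into the primary comparison, unmarked, and any effect could favour only the AI. The size is unknown. The 0.4-1.8 points rest on assumed overlap of 10-20% and assumed accuracy of 95-100% in those people, and are an illustration, not an estimate. Actual overlap may be zero. The case for acting is that the bias runs toward the sponsor's hoped-for conclusion, is hard to rule out after the results are known and is easy to prevent beforehand.

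The re-entry point is minor. The plan most naturally reads as one pass per person and needs only a sentence to say so.

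**What to change.** 1. In 4.3, add a screening check of each participant against the development-data logs of the two earlier studies, and record the result as a flag on the case report form. Identify the model version and cutoff to which the check applies.
2. In 7.3.5, exclude from the primary AI-human comparison anyone whose images were used to train the evaluated model, tune it or set its cutoff. Add a sensitivity analysis that includes them. They may still be enrolled for the other objectives.
3. In 3.2 or 4.2, state that each person takes part in only one of Phases 0-3.

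The cost is a log check, one data item and a smaller primary set, possibly with fewer Fitzpatrick IV-VI participants, because the clinic stream is screened for those types. On the assumptions in section 7.1, 130 positive sites at 1.5 per participant need 130/1.5 = 86.7, so 87 participants. Up to 13 of the 100 in Phase 1 could then be set aside without falling below that target. At 20% overlap, 80 × 1.5 = 120 sites would remain, and some replacement enrolment would be needed. If positives occur at the earlier trial's rate (132/206 = 0.64 per participant), the target is missed with or without this exclusion, and each person set aside adds a little to the shortfall.
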